7. PLANNED ANALYSIS

Safety analysis (refer to [Section 7.8](#)) will be performed by [REDACTED] and will be presented in Sections 15.1 to 15.4 of the CTR and in Appendix 16.2 and 16.1.13.1.

Statistical model-based analysis of PK endpoints will be performed by [REDACTED] and will be presented in Section 15.5 of the CTR and in Appendix 16.1.13.3.

Descriptive data analysis of PK endpoints and concentrations will be performed by the [REDACTED] at [REDACTED] and will be presented in Section 15.6 of the CTR and in Appendix 16.1.13.5.

Descriptive data analysis of PD/biomarker parameters will be performed by [REDACTED] and will be presented in Section 15.7 of the CTR and Appendix 16.1.13.6.

The format of the listings and tables will follow the BI standards (see BI-KMED-BDS-HTG-0045 [\(6\)](#)) with the exception of those generated for PK-calculations following BI standards for PK/PD analysis [\(7\)](#).

The individual values of all subjects will be listed, sorted by treatment group, subject number and visit. The listings will be included in Appendix 16.2 of the CTR.

No inferential statistical interim analysis is planned.

For end-of-text tables, the set of summary statistics for non-PK and non-PD parameters is:

N	number non-missing observations
Mean	arithmetic mean
SD	standard deviation
Min	minimum
Median	median
Max	maximum

For analyte concentrations, PK and PD parameters, the following descriptive statistics will additionally be calculated:

Nobs	number of observations
CV	arithmetic coefficient of variation
gMean	geometric mean
gCV	geometric coefficient of variation
P10	10th percentile
Q1	1st quartile
Q3	3rd quartile
P90	90th percentile

The data format for descriptive statistics of concentrations will be identical to the data format of the respective concentrations. The descriptive statistics of PK and PD parameters will be calculated using the individual values with the number of decimal places as provided by the

evaluation program. Then the individual values as well as the descriptive statistics will be reported with three significant digits in the CTR.

Tabulations of frequencies for categorical data will include all possible categories available in the CRF and will display the number of observations in a category, as well as the percentage (%). Percentages will be rounded to one decimal place and will be based on all subjects in the respective subject set whether they have non-missing values or not. The category 'missing' will be displayed only if there are actually missing values.

Units of variables should be given in the titles or column/row descriptors in brackets (e.g. (mg)).

Exclusion of PK and PD parameters

The ADS “ADPP” (PK parameters) and “ADYP” (PD parameters) contain column variables APEXC and APEXCO indicating inclusion/exclusion (APEXC) of a PK or PD parameter and an analysis flag comment (APEXCO). All analyses based on the PKS or PDS, respectively, will include parameters only if they are not flagged for exclusion, that is APEXC is equal to “Included”.

Exclusion of PK and PD concentrations

The ADS “ADPC” (PK concentrations per time-point or per time-interval) and “ADYC” (PD concentrations per time-point or per time-interval) contains column variables ACEXC and ACEXCO indicating inclusion/exclusion (ACEXC) of a concentration and an analysis flag comment (ACEXCO). Exclusion of a concentration depends on the analysis flag comment ACEXCO. For example, if ACEXCO is set to ‘ALL CALC’, the value will be excluded for all types of analyses based on concentrations. If ACEXCO is set to ‘DESC STATS’ the value will be excluded from descriptive evaluations per planned time point/time interval. If ACEXCO contains the addition ‘TIME VIOLATION’ or ‘TIME DEVIATION’ the value can be used for further analyses based on actual times. If ACEXCO is set to ‘HALF LIFE’, the value will be excluded from half-life calculation (and, as a consequence, any calculation that relies on λ_z) only; the value is included for all other analyses.

Further details are given in *BI-KMED-TMCP-MAN-0014* “Noncompartmental Pharmacokinetic / Pharmacodynamic Analyses of Clinical Studies” (5) and *BI-KMED-TMCP-MAN-0010*: “Description of Analytical Transfer Files and PK/PD Data Files” (8).

7.1 DEMOGRAPHIC AND OTHER BASELINE CHARACTERISTICS

Only descriptive statistics are planned for this section of the report, based on the TS. The data will be summarised by treatment group and in total.

7.2 CONCOMITANT DISEASES AND MEDICATION

Frequency tables are planned for this section of the report, based on the TS.

Concomitant diseases will be coded using the coding system of the Medical Dictionary for Drug Regulatory Activities (MedDRA). Medications will be coded using the World Health Organization Drug Dictionary (WHO-DD). The coding version number will be displayed as a footnote in the respective output.

The diagnoses and medications will be listed. Subjects without any concomitant diagnoses or concomitant therapies will be marked with a “No” in the respective column.

The relevance of the concomitant therapies to the evaluation of PK will be decided no later than at the RPM.

7.3 TREATMENT COMPLIANCE

Section 4.3 of the CTP: *Compliance will be assured by administration of all trial medication in the study centre under supervision of the investigating physician or a designee. The measured plasma concentrations and/or urinary excretion of trial medication will provide additional confirmation of compliance.*

It is not intended to list the compliance separately. Any deviations from complete intake will be addressed in the RPM (cf. TSAP [Section 6.2](#)) and described in the CTR.

7.4 PRIMARY ENDPOINT

Refer to TSAP [Section 7.8](#) for a description of the analysis of the primary endpoint.

7.5 SECONDARY ENDPOINTS

7.5.1 Key secondary endpoints

This section is not applicable as no key secondary endpoint has been specified in the protocol.

[figure not shown]
7.5.2 (Other) Secondary endpoints

Section 7.3.2 of the CTP:

Primary analyses

The secondary endpoints (refer to CTP Section 2.1.3) will be analysed descriptively.

This figure is a 2D grayscale heatmap representing a distribution of data points. The horizontal axis (x-axis) and vertical axis (y-axis) both range from 0 to 100, with major tick marks at 0, 50, and 100. The distribution is primarily concentrated in a central region, with a main peak at approximately (50, 50) and a secondary, smaller peak at approximately (75, 75). The distribution is relatively uniform within these peaks but shows a gradual decrease in intensity as it moves away from the center, with the lowest values occurring at the outer edges of the plot area.

7.7 EXTENT OF EXPOSURE

Descriptive statistics are planned for this section of the report based on the TS. The date and time of drug administration will be listed for each subject.

7.8 SAFETY ANALYSIS

All safety analyses will be performed on the TS except for the exposure-response analyses, which are based on the ECGPCS.

The safety data for treated subjects who failed to complete the study (dropouts or withdrawals) will be reported as far as their data are available. All withdrawals will be documented and the reason for withdrawal recorded.

7.8.1 Adverse Events

AEs will be coded with the most recent version of MedDRA.

Unless otherwise specified, the analyses of AEs will be descriptive in nature. All analyses of AEs will be based on the number of subjects with AEs and NOT on the number of AEs. BI standards as presented in “Analysis and Presentation of Adverse Event Data from Clinical Trials – Display Template” [BI-KMED-BDS-HTG-0041] (9) and [BI-KMED-BDS-HTG-0066] (10) will be applied.

The analysis of AEs will be based on the concept of treatment emergent AEs. That means that all AEs will be assigned to ‘screening’, ‘on treatment’ or ‘follow-up’ phases as defined in Section 6.1. AEs will be analysed based on actual treatments, as defined in Table 6.1: 1.

According to the clinical study protocol, adverse events of special interest (AESI) will be analysed:

Section 5.2.6.1.4 of the CTP: *The following are considered as AESIs:*

- **Hepatic injury**
A hepatic injury is defined by the following alterations of hepatic laboratory parameters:
 - o *An elevation of AST (aspartate transaminase) and/or ALT (alanine transaminase) ≥ 3 -fold ULN combined with an elevation of total bilirubin ≥ 2 -fold ULN measured in the same blood sample, or*
 - o *Aminotransferase (ALT, and/or AST) elevations ≥ 10 fold ULN*

According to ICH E3 (11), in addition to Deaths and Serious Adverse Events, ‘other significant’ AEs need to be listed in the clinical trial report. These will be any non-serious adverse event that led to an action taken with study drug (e.g. discontinuation or dose reduced or interrupted).

An overall summary of AEs will be presented.

The frequency of subjects with AEs will be summarised by treatment, primary system organ class (SOC) and preferred term (PT). Separate tables will be provided for subjects with serious AEs, for subjects with drug-related AEs, for subjects with drug-related serious adverse events and for subjects with AESIs. In addition, the frequency of subjects with AEs will be summarised by treatment, worst intensity, primary system organ class (SOC) and preferred term (PT).

The system organ classes will be sorted alphabetically, PTs will be sorted by frequency (within SOC). The MedDRA version number will be displayed as a footnote in the respective output.

In addition, frequencies of subjects with non-serious AEs that had an incidence of $> 5\%$ for at least one treatment will be summarised by treatment, primary SOC and PT.

7.8.2 **Laboratory data**

The analyses of laboratory data will be descriptive in nature and will be based on BI standards [BI-KMED-BDS-HTG-0042] (12). Analyses will be based on normalised values, which means transforming to a standard unit and a standard reference range. The original values will be analysed if the transformation into standard unit is not possible for a parameter.

Laboratory data will be analysed qualitatively via comparison of laboratory data to their reference ranges. Values outside the reference range as well as values defined as possibly clinically significant will be flagged in the data listings.

Clinically relevant findings in laboratory data will be reported as baseline conditions (at screening) or as AEs (during the trial) if judged clinically relevant by the investigator, and will be analysed as such.

It is the investigator's responsibility to decide whether a lab value is clinically significantly abnormal or not (at the RPM at the latest).

Descriptive statistics of laboratory data including change from baseline will be calculated by planned time point based on the worst value of the subject at that planned time point (or assigned to that planned time point).

7.8.3 Vital signs

Descriptive statistics over time including change from baseline will be performed for vital signs (blood pressure and pulse rate). In the listing the change from baseline will also be displayed. For vital signs, descriptive statistics will be calculated by planned time point based on the last value of the subject at that planned time point (or assigned to that planned time point), and will be displayed by treatment and in total.

Descriptive statistics over time including change from baseline (by treatment and in total) will also be provided for the orthostatic test results to enable checking of orthostatic hypotension occurrence. Subjects should have spent at least 5 minutes in the supine position before blood pressure and pulse rate will be measured the first time. Further 2 measurements will be performed immediately after standing up and after 3 minutes in a standing position. An orthostatic hypotension is defined as a decline in systolic blood pressure of ≥ 20 mmHg or a decline in diastolic blood pressure of ≥ 10 mmHg within the first three minutes after standing up. Orthostatic hypotension is assessed for all post dose time points.

Body temperature will be listed only.

Clinically relevant findings will be reported as baseline conditions (at screening) or as AEs (during the trial) if judged clinically relevant by the investigator, and will be analysed as such.

7.8.4 ECG

Continuous safety ECG monitoring (by investigator)

Clinically relevant abnormal findings will be reported as adverse events.

No separate listing or analysis of continuous ECG monitoring will be prepared.

12-lead ECG

Abnormal findings will be reported as baseline conditions (at screening) or as AEs (during the trial) if judged clinically relevant by the investigator. All evaluations of ECG data will be based on the TS, except the exposure-response analyses, which are based on the ECGPCS set.

Listing of individual data

For all quantitative endpoints, listings of individual data will be shown in Appendix 16.2. For QTcB and RR, only listings will be provided. Occurrences of notable findings will be flagged. Comments regarding the ECGs will be listed.

Categorical endpoints

For the categorical endpoints, frequency tables will be provided.

For all subjects with any notable finding in ECG intervals, a separate listing will be created as end-of-text display (based on the same display template as in Appendix 16.2), and the corresponding time profiles will be shown.

Quantitative endpoints

Descriptive statistics (N, mean, SD, min, median, max) will be provided for the absolute values and changes from baseline over time of QTcF, QT, HR, PR and QRS. The time profiles of mean and SD for the changes from baseline on treatment will be displayed graphically by treatment.

For QTcF and HR changes from baseline, the relationship to the corresponding plasma concentrations will be evaluated using a random coefficient model. For subjects in the ECGPCS, all time points with available ECG endpoints and valid time-matched drug plasma concentrations will be included. For the handling of missing values, see [Section 6.6](#).

The response variable will be the change from baseline in QTcF (Δ QTcF). The placebo subjects will be included in the analysis, setting their plasma concentrations to zero.

As a first step, it is investigated if there is a potential delayed or accelerated (e.g. due to metabolites) effect of the drug on QTcF. A general visual impression will be provided by overlaying time profiles of plasma concentrations and QTcF changes from baseline (Δ QTcF). These figures will be generated for each subject (presented in the Statistical Appendix of the CTR), as well as for means per treatment group (presented in the End-of-Text part of the CTR).

The relationship between BI 474121 plasma concentrations and QTcF changes from baseline will be investigated in an exploratory manner using a random coefficient model to estimate the difference in means between BI 474121 and placebo of QTcF change from baseline and its 90% confidence interval at the geometric mean of C_{max} after single dose. Additionally, the estimated overall slope with its 90% confidence interval will be provided. The used random coefficient model is based on a white paper from Garnett et al. (13) with Δ QTcF as response variable, centered baseline QTc and plasma concentration as continuous covariates and treatment as fixed categorical effects, and a random intercept and slope for each subject. Restricted maximum likelihood estimation will be performed, and the Kenward-Roger

method will be applied to adjust standard errors and estimate denominator degrees of freedom. For more details refer to [Section 10.1.4](#).

For visualization, a scatterplot of the BI 474121 plasma concentration against the following individual QTcF values will be provided: For each subject on active treatment and each time point, subtract the mean value of all individual observed Δ QTcF values from the placebo group for this time point from the individual observed Δ QTcF value for this subject and time point. This results in estimates for “individual $\Delta\Delta$ QTcF” values, which should only be used for plotting purposes. The corresponding regression line and its pointwise confidence bands as well as and the geometric mean of C_{max} and $C_{max,ss}$ for each dose will additionally be displayed in the plot.

The goodness of fit of the above model will be checked. The visual checks will include the inspection of concentration-QTcF quantile plots (13) and residual plots. In case of non-linearity or if there is evidence for a delayed effect, further models will be explored in order to better characterise the PK-ECG relationship.

All of the above described graphical and statistical analyses will be also performed for HR in place of QTcF.

Appropriateness of heart rate correction methods of QT interval

To evaluate the appropriateness of the heart rate correction methods, the slope of the relationship of QTcF interval versus RR interval will be estimated separately for off-drug values and active treatment, by applying the random coefficient model described in [Section 10.1.2](#) using the QTcF and RR variable values per time point. A scatterplot of QTcF vs RR including the overall regression lines will be included in the Statistical Appendix of the CTR.

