### **1.3.2 Maximum dose**

The maximum dose of this trial is 20 mg and this dose will not be exceeded in this trial.

Therapeutic systemic exposure of BI 474121 at steady state has been projected to be 24 nmol/L ( $C_{max,ss}$ ) and 302 nmol·h/L ( $AUC_{\tau,ss}$ ). It is planned to explore higher exposures (doses) for several reasons.

Proprietary confidential information © 2021 Boehringer Ingelheim International GmbH or one or more of its affiliated companies

First, subsequent clinical studies in patients may show that the required therapeutic doses and exposures are significantly higher than predicted. Also, higher doses / exposures might be required for more severe disease states, i.e. while higher doses and exposures may still be well tolerated, they provide a larger magnitude of therapeutic effects.

Second, testing of doses higher than 2.5 mg is justified to account for uncertainties in translation from preclinical data to human.

Third, even if eventually the therapeutic dose turns out to be as low as 2.5 mg, higher than therapeutic doses and exposures are typically explored in the well-controlled clinical environment of phase I trial, if supported by the currently available safety data, in order to provide a sufficient safety margin for potential subsequent trials, e.g.

- To cover exposures eventually reached in trials with multiple dosing and accumulation
- To cover exposures eventually reached in trials in patients with impaired excretion function, such as renal / hepatic impairment, where substantial increases in exposure may be seen
- To cover exposures eventually reached in subsequent drug-drug interaction trials
- To derive a safe supra-therapeutic dose for a thorough QT (tQT) trial or to achieve high enough exposures to waive a tQT trial

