6. GENERAL ANALYSIS DEFINITIONS

6.1 TREATMENTS

For basic study information on investigational products, assignment to treatment groups and selection of doses, please see CTP Sections 3 and 4.

It is planned that 32 healthy Japanese male subjects participate in this randomized, double-blind, placebo-controlled study. The subjects will be assigned to one of 4 dose groups consisting of 8 subjects per group, and will be randomized to placebo or active treatment within their dose group. Within each dose group, 6 subjects will receive a single dose of active drug and 2 subjects will receive a single dose of placebo.

Table 6.1: 1 Treatments and labels used in the analysis

Treatment	Label in dataset	Short label
P	Placebo#	Placebo
A	BI 474121, tablet, 2.5 mg, po, qd	BI 2.5mg
B	BI 474121, tablet, 2*2.5 mg, po, qd	BI 5mg
C	BI 474121, tablet, 10 mg, po, qd	BI 10mg
D	BI 474121, tablet, 2*10 mg, po, qd	BI 20mg

#For data analysis purposes, the placebo group will consist of all subjects treated with placebo, regardless of the dose group in which they were treated.

Section 1.2.7 of CTP:

The Residual Effect Period (REP) of BI 474121, when measurable drug levels and/or pharmacodynamic effects are still likely to be present, is not known. Conservatively (...) a REP of 7 days is assumed, i.e. the individual subject's end of trial is on Day 8-15 following dosing with investigational drug.

The following study phases will be defined for the analysis of AEs:

- **Screening** (ranging from 0:00h on day of informed consent until first administration of study medication)
- **On treatment** (ranging from the time of first administration of study medication (BI or Placebo) until 168 hours (7 days) after time of administration)
 - ➔ Labelled Placebo, BI 2.5mg, BI 5mg, BI 10mg, BI 20mg
- **Follow-up (F/U)** (ranging from 168 hours (7 days) after administration of BI or Placebo until 0:00 h on the day after trial termination date)
 - ➔ Labelled F/U

Section 7.3.4 of the CTP: *Note that AEs occurring after the last per protocol contact but entered before final database lock will be reported to Pharmacovigilance only and will not be captured in the trial database.*

Displays of AEs will be stratified by dose group as specified in [Table 6.1: 1](#). The following AE displays will be provided in the report:

Section 15.3 and Appendix 16.1.13.1.8 (for ClinicalTrials.gov) of the CTR displays:

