At Visits 1 and 3 (screening and end of trial examination), single ECGs will be recorded and will not be transferred to the central ECG lab. Three triplicate ECGs will be recorded as the baseline before drug administration, but only the first ECG of each of the 3 baseline triplicates will be transferred to the database. At all other time points (except for ECGs on day 4 and 5 of Visit 2), 1 triplicate ECG will be recorded, but only the first single ECG of the triplicate will be transferred to the database. The baseline value of an ECG variable is defined as the mean of the ECG variable values prior to drug administration.

For the exposure response analyses, pairs of ECG variables and corresponding plasma concentrations will be built using the same planned time points, e.g., the HR change from baseline and the plasma concentration measured at planned time 0:30 will build one pair. Whether a time deviation between PK blood sampling time and corresponding ECG recording is too big and the pair has to be excluded from the analysis will be decided no later than at the RPM. Data exclusion due to time deviations will only be applied to subjects on active study treatment.

In line with the tolerated time deviations of previous trials in this project, the acceptable maximum time deviations between ECG recordings and plasma concentration sampling are proposed to be

- 10 minutes for up to 1 hours (including) after dosing,
- 20 minutes for time points from more than 1 hour to 12 hours after dosing, and
- 60 minutes for time points at 12 hours or later after dosing,

Pairs with time deviations exceeding those specified above will be excluded from exposure-response analyses. When the sampling time of the blood sample or the ECG recording is not available, the pair will also be excluded.

As the clinical trial protocol permits larger time deviations of ECG measurements from the planned time in the flow chart, and consequently indirectly accepts larger time deviations of ECG and PK sampling, a sensitivity analysis will be done. For the sensitivity analysis, the acceptable maximum time deviation between ECG recording and plasma concentration sampling are proposed to be

- 15 minutes for up to 4 hours (including) after dosing,
- 30 minutes for time points from more than 4h to 24h after dosing,
- 60 minutes for time points at 24h to 48h after dosing,
- 120 minutes for time points at 48 hours or later after dosing.

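### SAP 7.8.4 lists no nominal-time effect in its concentration-QTcF and concentration-HR models; unless the non-public Section 10.1.4 adds one, a time course shared by all arms biases the reported slope (low priority)

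*SAP*

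**What the plan says.** SAP 7.8.4 gives the exposure-response model as a random coefficient model for the change from baseline in QTcF, with centred baseline QTc and "plasma concentration as continuous covariates and treatment as fixed categorical effects, and a random intercept and slope for each subject". It is fitted by REML with Kenward-Roger degrees of freedom. The section says that the model is based on a published white paper, and it refers to Section 10.1.4 for detail. The public SAP goes from Section 9 to Section 11, so Section 10.1.4 cannot be read.

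Two results are to be reported with 90% confidence intervals. One is the BI-minus-placebo difference at the geometric mean of Cmax. The other is the slope: "Additionally, the estimated overall slope with its 90% confidence interval will be provided".

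Four other statements matter:
- On placebo (SAP 7.8.4): "The placebo subjects will be included in the analysis, setting their plasma concentrations to zero".
- On pairing (SAP 6.7): "pairs of ECG variables and corresponding plasma concentrations will be built using the same planned time points".
- Placebo-corrected values per time point are computed, but these are values "which should only be used for plotting purposes" (SAP 7.8.4).
- On model extension (SAP 7.8.4): "In case of non-linearity or if there is evidence for a delayed effect, further models will be explored".

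All of this is repeated for heart rate. SAP 7.8.4 does not say whether treatment is coded as active/placebo or by dose. The table in SAP 6.1 headed "Treatments and labels used in the analysis" has five entries: placebo and four doses.

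**The concern.** The protocol Flow Chart puts dosing at about 08:00 for everyone. Protocol 4.2.2.2 allows no food for at least 4 h, and lunch follows. On Day 1, concentration in each active subject therefore moves with the clock, and so do posture, fasting, meals and any daily rhythm in QTcF or heart rate.

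Placebo subjects have the same clock but a concentration that never changes. Without a time term in the model, their time course cannot be used to remove the shared course from the slope. The treatment term shifts the mean of the active arms and does nothing to the within-subject association. The placebo correction that would help is reserved for the scatterplot. A shared time course is not among the stated triggers for further models.

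The sign of the bias depends on the unknown phase of the time course, so it could create a slope or hide one. Protocol 1.3.2 includes among its reasons for higher doses "to achieve high enough exposures to waive a tQT trial". No other analysis in the public text relates exposure to QTcF with a confidence interval.

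**Working it through.** The plan gives no figure for this analysis, so there is none to reproduce. The check asks how large the bias would be if exactly the listed terms were fitted.

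**Algebra.** Let f(t) be a time course common to all arms and C the concentration. In the simple case:
- bias of the slope: b = Cov(f, C) / Var(C), taken within active subjects;
- bias of the difference at Cmax: b × (Cmax − mean C), because the treatment term absorbs b × mean C.

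The slope thus takes the full bias and the difference only part of it. If f is uncorrelated with C over the sampled times, there is no bias, only noise.

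**Inputs from the documents.** 8 pooled placebo subjects and 6 per dose at 2.5, 5, 10 and 20 mg. 14 matched post-dose ECG/PK times from 0.5 to 96 h (SAP Table 6.7: 1 and the Flow Chart), so up to 32 × 14 = 448 observations. Baseline is the mean of −1:00, −0:45 and −0:30. Half-life is about 20 h (Protocol 1.4.3).

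**Assumed inputs.** One-compartment oral kinetics, absorption rate ka 1-3/h, exposure CV 25%, true drug effect zero. f is a 24-h cosine of 4 ms peak-to-trough (amplitude 2 ms), with its peak placed at each of the 24 clock hours. QTcF SDs: intercept 5 ms, slope 3 ms per 20 mg gMean Cmax, residual 7 ms.

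**Generalised least squares.** Bias = (X'V⁻¹X)⁻¹ X'V⁻¹f, and the difference is the treatment effect plus slope × gMean Cmax. The phase average is of absolute bias. Slope is in ms per 20 mg gMean Cmax; the lower end of each bias range is ka 3/h and the upper end ka 1/h. Coverage is of the nominal 90% interval from REML simulation (2,400 runs per cell, t with 28 df because Kenward-Roger was not available).

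| 4 ms swing, listed terms only | Five-level | Active/placebo |
|---|---|---|
| Slope, phase average | 1.14-1.75 ms (0.55-0.82 SE) | 1.03-1.58 ms (0.52-0.77 SE) |
| Slope, worst phase | 1.79-2.73 ms | 1.62-2.47 ms |
| Slope, coverage | 78-84% | 79-85% |
| Difference at 20 mg, phase average | 0.45-0.73 ms (0.14-0.23 SE) | 0.72-1.13 ms (0.27-0.42 SE) |
| Difference at 20 mg, worst phase | 0.71-1.14 ms | 1.13-1.76 ms |
| Difference at 20 mg, coverage | 90% | 87-89% |

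The difference carries 0.45/1.14 to 0.73/1.75, about 40%, of the slope bias with five-level coding, and 0.72/1.03 to 1.13/1.58, about 70%, with active/placebo coding. At the 2.5-10 mg gMean Cmax its phase-averaged bias is at most 0.34 ms.

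**Other settings.**
- No swing: all coverages are 89-91%.
- 8 ms swing: slope coverage 52-70% and 54-71%; difference 85-89% and 78-86%.
- Other SDs (intercept 3-8, slope 1.5-6, residual 5-10 ms) at 4 ms: phase-averaged slope bias 1.00-2.22 and 0.69-2.20 ms; difference 0.34-1.26 and 0.47-1.64 ms.
- Heart rate, assumed 6 bpm swing, SDs 4, 2 and 5 bpm, ka 1/h only (the larger-bias end): bias of the difference 1.07 and 1.70 bpm, its coverage 85% and 77%, slope coverage 48% and 51%.

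**With categorical nominal time added.** f lies in the span of the time effects, so the GLS bias is zero. Coverage is 91-92% for the difference and 89-91% for the slope at any swing. At ka 1/h the slope SE rises from 2.14 to 2.88 ms (five-level) or 2.05 to 2.64 ms (active/placebo).

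**Break-even in mean squared error** (slope, five-level, ka 1/h). Variance added: 2.88² − 2.14² = 3.71. Squared bias removed: the bias is a cosine in phase, so its mean square is half the squared worst case, 2.73²/2 = 3.73. The two balance at a swing of about 4 ms. Over ka 1-3/h, and for both quantities, break-even is about 4-6 ms.

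**The case against.** The strongest objection is that no omission is shown. The sentence in 7.8.4 is a summary, and the detail sits in a section that was removed before publication. Other SAP sections refer to 10.1.2 and 10.1.3 for a model and for handling rules, so Section 10 evidently holds such detail. The white paper cannot be consulted here either, and nothing is claimed about what it prescribes. This stands. A reader might infer that the plan leaves time out, but the public text supports only that 7.8.4 does not mention it.

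Second, the difference at gMean Cmax, which 7.8.4 names first as the model's purpose, is hardly harmed in the base case. This also stands, most clearly for five-level coding.

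Third, every size rests on assumption. The documents give no daily rhythm, absorption rate or SD. At a 4 ms swing the time term ranges from neutral to slightly worse in mean squared error. This stands, and is why the fix is a trade-off.

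Fourth, the planned profiles by treatment, concentration overlays and residual plots could reveal a shared pattern, and a rhythm out of phase with concentration might be taken for a delayed effect and trigger further models. This is partly right. These displays may show the problem, but they do not correct the slope, the difference or their intervals.

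The confounding is also incomplete: the 24, 48, 72 and 96 h samples fall at 08:00 too, and dose spans 8-fold. Both features are already in the calculation.

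**Conclusion.** The point holds conditionally. If the listed terms are the whole model, the reported slope and its 90% interval are exposed to any QTcF or heart-rate time course shared by the arms and correlated with concentration. Under the base-case assumptions the slope interval covers about 78-85% instead of 90%. Bias scales in proportion to the assumed swing.

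Two stronger readings should be resisted. One is that the BI-minus-placebo difference is materially wrong: at 4 ms its bias is 0.14-0.42 SE depending on coding, and coverage falls to 87% at worst. The other is that a decision on a thorough QT trial rests on this model: Protocol 1.3.2 uses that aim to justify exposures and does not name the analysis.

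The analysis is labelled exploratory, Protocol 7.2 plans no hypothesis tests, and no primary or secondary endpoint or stopping rule uses the model. Priority is low.

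**What to change.** Check Section 10.1.4.
- If it already contains nominal time, amend 7.8.4 to say so.
- If it does not, add categorical nominal post-dose time (14 matched time points) as a fixed effect in both the QTcF and heart-rate models. Report the slope and the difference at gMean Cmax from that model, and keep the listed model as a sensitivity analysis.
- In either case, state in 7.8.4 whether treatment is active/placebo or five-level, in agreement with 10.1.4.

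Cost: 13 degrees of freedom out of up to 448 observations, and no new data. The slope SE rises by about 28-35%. At ka 1/h the SE of the difference rises from 3.16 to 3.27 ms (five-level) or 2.68 to 2.93 ms (active/placebo). The return is protection from bias and an interval that holds its level; precision improves overall only if the shared swing exceeds about 4-6 ms.
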